### **5.4** Tumor Evaluation Visits

Disease status and tumor response will be assessed in eight-week intervals up to one year after starting therapy (calculated from the first dose of BBI608) or as clinically indicated. Standard

imaging studies should be performed according to institutional procedures. Tumor response for solid tumors will be evaluated using the guidelines for Response Evaluation Criteria in Solid Tumors (RECIST 1.1) outlined in Section 9.

Once progression of disease during therapy is documented, patients must be taken off treatment and may receive any therapy as determined by their treating physician.

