#### **Study Design:**

This is an open label, multi-center, Phase II study of BBI608 administered in combination with either Cetuximab, or Panitumumab, or Capecitabine. A cycle will consist of daily and continuous oral administration of BBI608 for four weeks in combination with either Cetuximab, or Panitumumab, or Capecitabine.

Arm A (Cetuximab) - BBI608 is administered at 480 mg po twice daily continuously and Cetuximab will be administered IV on day 5 at 400 mg/m² intravenous infusion over 120 minutes as the initial dose, then weekly at 250 mg/m² over 60-minutes at subsequent cycles.

Arm B (Panitumumab) - BBI608 is administered at 480 mg po twice daily continuously and Panitumumab will be administered IV on day 8 and 22 of each 28 day cycle at 6 mg/kg over 60 minutes.

Arm C (Capecitabine) - BBI608 is administered at 480 mg po twice daily continuously and Capecitabine will be administered orally at  $1000 \text{ mg/m}^2$  bid daily on days 8-21 every three weeks.

6 patients will be initially enrolled in each combination arm at a dose level of 480 mg twice daily (960 mg total daily dose) BBI608. If  $\leq 1$  out of 6 patients have an observable DLT in the combination regimen, then that combination arm may continue to accrue patients. If DLT occurs in  $\geq 2$  of the 6 patients in a combination arm, then the combination arm will closed and no new patients will be enrolled into this combination arm. A trial arm of BBI608 in combination with Cetuximab, or Panitumumab, or Capecitabine will continue to enroll patients only if no more than 1 out of 6 patients for each combination has an observable DLT. It is expected that approximately 60 to 80 CRC patients will be enrolled in the study.

Pharmacokinetics (PK) will be performed in the first cycle for the initial 6 patients of each combination arm of the study.

Pharmacodynamic assessments will be performed in patients with accessible tumors when tumor biopsy is possible.

Evaluation of anti-tumor activity of BBI608 in combination with Cetuximab, or Panitumumab or Capecitabine will be performed at about 8 week intervals while patients remain on study.

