### 4 INVESTIGATIONAL PLAN

# 4.1 Overall Study Design

This is an open-label, multicenter Phase II study of oral BBI608 administered with Cetuximab, or Panitumumab, or Capecitabine to patients with advanced metastatic colorectal cancer. The study is based on a Simon 2-stage design that will examine the safety, tolerability and pharmacokinetics of BBI608 and Cetuximab, or Panitumumab, or Capecitabine, and assess the preliminary anti-tumor activity of BBI608 when administered in combination with Cetuximab, or Panitumumab, or Capecitabine in patients with advanced colorectal cancer.

BBI608 treatment will be at a dose level of 480 mg twice daily (960 mg total daily dose). In each cycle, BBI608 will be taken daily continuously for 4 weeks (28 days). BBI608 will be administered twice daily approximately one hour prior to or two hours after meals with the first dose given in the morning and approximately 12 hours between doses.

For patients receiving Cetuximab therapy, Cetuximab will be administered IV on day 5 of cycle 1 at 400 mg/m² intravenous infusion over 120 minutes as the initial dose, then weekly at 250mg/m² over 60-minutes at subsequent cycles.

For patients receiving Panitumumab therapy, Panitumumab will be administered IV on day 8, and 22 of each 28 day cycle at 6 mg/kg over 60 minutes.

For patients receiving Capecitabine therapy, Capecitabine will be administered orally at 1000 mg/m^2 bid daily on days 8-21 every three weeks.

Cycles will be repeated until progression of disease, unacceptable toxicity, or another discontinuation criterion is met. In the case of toxicity, adjustment is permitted. If administration of Cetuximab, or Panitumumab, or Capecitabine is discontinued due to Cetuximab, or Panitumumab, or Capecitabine-related toxicity, administration of BBI608 will be continued until disease progression if tolerated.

Initially, 6 patients will be enrolled in each combination arm at a dose level of 480 mg twice daily (960 mg total daily dose) BBI608. If  $\leq 1$  out of 6 patients has an observable DLT in the combination regimen, then that arm of the study will continue to enroll patients at 480 mg po twice daily (960 mg total daily dose) of BBI608 following the Simon 2-stage design (see Table 1). If

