## 5.5 End of Study Evaluation

All patients will be followed for a minimum of 30 days after the last dose of BBI608. If a patient is removed from the study due to drug-related adverse events, the patient will be followed until resolution of any drug-related AE occurring during the study or within 30 days of the last BBI608 dose, or for 30 days, whichever is longer. In the presence of toxic effects, follow-up visits will be required every four weeks until all study related toxicities have resolved to baseline (or < Common Terminology Criteria for Adverse Events [CTCAE] Grade 1), stabilized or are deemed irreversible.

The following assessments will be made during the end of study visit:

- Physical examination
- Karnofsky performance status
- Vital signs (weight, temperature, blood pressure, respiration and pulse)
- Hematology (see Section 6.3)
- Blood chemistry (see Section 6.3)
- Liver function tests (see Section 6.3)
- Electrolytes (see Section 6.3)
- Urinalysis (see Section 6.3)
- 12-lead ECG
- Tumor marker, if applicable
- Tumor biopsy, if applicable (see Section 6.5.1)
- Tumor measurement and staging
- Assess adverse events
- Record concomitant medications

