# 14 APPENDIX A: SCHEDULE OF ASSESSMENTS

### BBI608 + Cetuximab

lv Visit			om last dose																				
End of Study Visit			≤30 days from last BBI608 dose			X		X	×	X	X	X	X	X	X	X	X		$\mathbf{X}^{7}$	X	X		
	pu	4	26																				•
	Cycle 2 & Beyond	3	19	± 1 day																			>
	ycle 2 &	2	12	# 1																			>
ns 	С	1	S.			×		×	×	×	×	×	×	×		×				X	X	X	>
Study Evaluations 		4	26					×	×	×	×	×	×	×				×		X	X	×	×
udy Ev		3	19					×	×	×	×	×	×	×						X	X	×	×
St	Cycle 1	2	12	± 1 day				X	×	×	X	×	×							X	X	X	×
	Cy		∞	#													X						
		1	S					×	×	×	×	×	×	×				X		X	X	X	×
			1												×							X	
Pre-Study	Evaluation	0	0	-7 ± 3 days	X	×	X	X	×	X	X	X	X	X	X	X	X		$X^6$	X			
Tests & Procedures		Week	Day	Window	Medical history	Physical examination	Serum pregnancy test 	Karnofsky performance status	Vital signs, Weight	Hematology 	Blood chemistry 	Liver function tests 	Electrolytes 	Urinalysis 	12-Lead electrocardiogram	Tumor markers 	Tumor biopsy 	Pharmacokinetics (first 6 patients only)	Tumor measurement & staging 	Concomitant medications	Adverse events 	Dispense BBI608	Cetuximah infusion

<sup>1 Calculated from the date of first BBI608 dose.
 Refer to Section 6.3 for description of laboratory assessments.
 If applicable

<sup>4 Including tumor measurements, following RECIST 1.1.
 Prior to cycle 3 and every other cycle thereafter, assessments must be made utilizing the same imaging method as baseline

<sup>6. Unless CT/MRI has been performed within last three weeks . Unless CT/MRI has been performed within last four weeks. . Patients will be followed until resolution of any drug-related AE or SAE occurring during the study or within 30 days of last BBI608 administration.

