combination arm, patients assigned to sub-cohorts IA and IB would receive napabucasin at 240 mg twice daily (480 mg total daily dose) starting on Day 1 of Cycle 1. Intra-patient dose escalation of napabucasin to 480 mg twice daily (960 mg total daily dose) was allowed for patients in these cohorts as tolerated. Patients assigned to sub-cohorts IIA and IIB would receive napabucasin at 480 mg twice daily (960 mg total daily dose) starting on Day 1 of Cycle 1. In the event of toxicity, dose adjustment of napabucasin was permitted, as recommended in dose modification guidelines. Additionally, patients assigned to sub-cohorts IA and IIA would receive prophylactic anti-diarrheal treatment starting the day prior to Day 1 of Cycle 1. Patients assigned to sub-cohorts IB and IIB would receive anti-diarrheal treatment on an as-needed basis starting with development of diarrhea (ie, any occurrence greater than the patient's baseline). For each combination regimen, patients would be sequentially assigned to each of the 4 sub-cohorts in the following order until 6 patients were accrued in each of the sub-cohorts: IA, IB, IIA, and IIB. If required, up to an additional 20 patients might be assigned to selected sub-cohorts to validate the observations in the initial 6 patients.

Sub-cohort	Napabucasin Starting Dose Level	Anti-diarrheal Administration*
IA	240 mg bid (480 total daily dose) ¹	Prophylactic
IB	240 mg bid (480 total daily dose) ¹	As needed
IIA	480 mg bid (960 total daily dose) ²	Prophylactic
IIB	480 mg bid (960 total daily dose) ²	As needed

Table 1 Tolerability Analysis of Napabucasin

¹Intra-patient dose escalation of napabucasin to 480 mg po twice daily (960 mg total daily dose) is allowed as tolerated. ²In case of toxicity, dose adjustment of napabucasin is permitted.

*See protocol amendment 2 [5] section 7.1.4 for details

A study cycle would consist of 28 days of daily administration of napabucasin in combination with cetuximab or panitumumab, or capecitabine. Cycles would continue until unacceptable toxicity, disease progression (clinical or radiological) or another discontinuation criterion is met. Pharmacokinetic (PK) assessments would be performed on the first 6 patients enrolled in each combination arm. Pharmacodynamic assessments would be performed in patients with readily accessible tumor tissue through an optional tumor biopsy. Evaluation of anti-tumor activity would be performed at 8-week intervals per RECIST 1.1 while patients remain on study.

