Appendix 1.3. Censoring for Time to Event Data

Table A.1.3.1 summarizes the censoring rules for the PFS analysis and displays censoring hierarchy for this study. Table A.1.3.2 shows the general reasons for PFS censoring and where the censoring hierarchy in Table A.1.3.1 came from.

Table A.1.3.1 PFS Censoring Reasons and Hierarchy

Censoring Hierarchy	Situation	Date of Event or Censor	Event / Censor
1	No baseline radiological tumor assessment available	Date of First Dose	Censored
2	New anticancer treatment started and no tumor progression	Date of previous adequate radiological assessment immediately prior to start of new therapy	Censored
3	Tumor progression (per RECIST 1.1) documented after 2 scan intervals following previous adequate radiological tumor assessment	Date of previous adequate radiological assessment	Censored
4, 5	No tumor progression (per RECIST 1.1) and patient lost to follow-up or withdrawal of consent	Date of last adequate radiological Assessment	Censored
6	No post baseline radiological tumor assessment available and no death reported within 2 scan intervals following the date of the first dose of study drug (napabucasin)	Date of First Dose	Censored
	No post baseline radiological tumor assessment available but death reported within 2 scan intervals following the date of the first dose of study drug (napabucasin)	Date of Death	Event
7	No tumor progression (per RECIST 1.1) and no death reported within 2 scan intervals following last adequate radiological tumor assessment	Date of last adequate radiological tumor assessment	Censored
	No tumor progression (per RECIST 1.1) but death reported within 2 scan intervals	Date of death	Event

following last adequate radiological tumor assessment		
Tumor progression (per RECIST 1.1) documented within 2 scan intervals following previous adequate radiological tumor assessment	Earliest of the target, non- target and new tumor assessment dates	Event

Notes: (1) Symptomatic deteriorations (ie, symptomatic progressions, which are not radiographically confirmed) will not be considered as progressions.

(2) If target, non-target and new lesion assessments have different dates within a visit, then the earliest of those dates will be considered as the date of the tumor assessment if the assessment for that visit is progressive disease (PD); otherwise the latest date will be used.

(3) Adequate radiographical tumor assessment refers to an assessment with overall response of CR, PR, SD, or PD.

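### Protocol 5.4 caps 8-weekly tumor assessment at one year while three other places do not; if the cap is followed, the SAP's censoring rule distorts the tail of the PFS curve

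*Protocol*

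**What the plan says.** The duration of tumor assessment is stated in four places.

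- Protocol 5.4: "Disease status and tumor response will be assessed in eight-week intervals up to one year after starting therapy". The same sentence goes on: "calculated from the first dose of BBI608) or as clinically indicated".
- Protocol synopsis, Study Design: evaluation "will be performed at about 8 week intervals while patients remain on study".
- Protocol Appendix A, footnote 5, in the schedules for all three arms: "Prior to cycle 3 and every other cycle thereafter, assessments must be made utilizing the same imaging method as baseline". Two 28-day cycles make 8 weeks, and no end is given.
- SAP 2.1: "performed at 8-week intervals per RECIST 1.1 while patients remain on study".

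Treatment has no one-year stop. Protocol 4.1: "Cycles will be repeated until progression of disease, unacceptable toxicity, or another discontinuation criterion is met". The PFS definitions (Protocol 10.4, SAP 3.2) have no time limit either. Protocol 5.5 also lists "Tumor measurement and staging" at the end-of-study visit; Appendix A footnote 7 waives it if a scan was done in the previous four weeks.

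For PFS, SAP Table A.1.3.1 (hierarchy 3) censors the following case at the date of the previous adequate assessment: "Tumor progression (per RECIST 1.1) documented after 2 scan intervals following previous adequate radiological tumor assessment". Table A.1.3.2 sets the gap at more than 16 weeks + 1 day and words the condition for any event. Progression or death inside the gap counts as an event. Symptomatic progression without radiographic confirmation does not.

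**The concern.** A site working from 5.4, the section devoted to tumor evaluation, could stop routine scans after the week-48 scan. A site working from Appendix A would continue. PFS could then be ascertained differently from site to site in patients on study beyond a year.

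The SAP's missed-assessment rule is built for an 8-weekly schedule that goes on. Once no scan is scheduled, the rule treats the absence of scans as missed assessments. A progression that is found and documented late is then removed as an event and the patient is censored back at week 48. Whether and where the patient is censored depends on when the event occurs, so the censoring is informative. At stake is the tail of a named secondary endpoint, where any long-lasting benefit would be read.

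**Working it through.** **1. The SAP's own figure.** Two scan intervals × 8 weeks = 16 weeks, plus a 1-day allowance, gives 16 weeks + 1 day. This reproduces the threshold in Table A.1.3.2.

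**2. Last scheduled scan under each reading.**
- With the 5.4 cap, 8-week steps within 365 days fall at weeks 8, 16, 24, 32, 40 and 48, so the last is week 48.
- With no cap (synopsis, Appendix A, SAP 2.1), scans go on at weeks 56, 64, 72 and so on. The gap stays at 8 weeks for a patient who attends, and hierarchy 3 does not apply.

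**3. Censoring threshold under the cap.** Week 48 + 16 weeks + 1 day = week 64 + 1 day (64.14 weeks). With no adequate scan in between:
- progression or death from week 48 to week 64 + 1 day is an event;
- progression or death after that is censored at week 48. For example, progression first seen on a symptom-triggered or end-of-study scan at week 70 is found but not counted.

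**4. How many patients are exposed.** Inputs: Protocol 1.4 gives PFS of 13 weeks (phase I colorectal patients) and 7.7 weeks (historical control). Treating these as medians is an assumption, as are the exponential form and the 20- and 26-week medians, which only show the range. Arm sizes are 24 (cetuximab, panitumumab) or 18 (capecitabine), with optional expansion to 50 (Protocol 4.1, Table 1). The formula is S(t) = 0.5^(t/median).

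| Median (weeks) | S(48) | S(64.14): exposed | of 50 | of 24 |
|---|---|---|---|---|
| 7.7 | 1.3% | 0.3% | 0.2 | 0.1 |
| 13 | 7.7% | 3.3% | 1.6 | 0.8 |
| 20 | 18.9% | 10.8% | 5.4 | 2.6 |
| 26 | 27.8% | 18.1% | 9.0 | 4.3 |

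The relevant column is S(64.14), not S(48). With a 13-week median, (0.0774 − 0.0327)/0.0774 = 58% of those event-free at week 48 have their event inside the window, where it still counts.

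**5. Direction of the distortion.** Suppose no scan is scheduled after week 48 and progression is imaged when it occurs. Everyone event-free past week 64 + 1 day is censored at week 48, so the risk set after week 48 holds only patients whose event falls inside the window. For t in that window, with c = 64.14, the Kaplan-Meier estimate tends to

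S(48) × [S(t) − S(c)] / [S(48) − S(c)].

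- Median 13, t = 60: 0.0774 × (0.0408 − 0.0327)/(0.0774 − 0.0327) = 0.014, against a true 0.041.
- Median 26, t = 60: 0.2781 × (0.2020 − 0.1809)/(0.2781 − 0.1809) = 0.060, against a true 0.202.

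At week 64 + 1 day the estimate reaches 0, against true values of 0.033 and 0.181. If instead no one is imaged and no one dies in the window, the curve ends at week 48.

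**6. What is not affected.** All four medians fall well before week 48, so the Kaplan-Meier median is essentially unchanged. For disease control rate, stable disease qualifies from 8 weeks − 1 day (SAP Appendix 1.2), long before the cap.

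**The case against.** The strongest reply is that the harm is conditional. Three of the four statements have no cap, and if sites follow them the gap never exceeds 8 weeks. The sentence in 5.4 also allows scans when clinically indicated, and a tumor measurement is required at the end of study. PFS is secondary and descriptive, no hypothesis test is planned, most patients are expected to be treated for 4 to 16 weeks (Protocol 4.6), and the PFS figures in the protocol are 7.7 and 13 weeks. All of this stands, and it is why the severity is low.

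It does not remove the point. A clinically indicated or end-of-study scan that shows progression after week 64 + 1 day is itself what hierarchy 3 censors. Only an intervening adequate scan without progression resets the clock, and 5.4 schedules none.

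Three stronger readings are tempting, and the documents do not support them.

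- *Late progression goes unscanned.* It only lacks a scheduled scan under 5.4, given the clinically-indicated clause and the end-of-study measurement. Nor are patients unobserved: monthly visits continue with physical examination and, where applicable, tumor markers (Protocol 5.3.3.6), and clinical progression is a ground for removal from study (5.6).
- *The SAP censors all progression after one year.* Events up to week 64 + 1 day count, and the clock runs from the last adequate assessment, whether scheduled or not.
- *The PFS tail is flattened, which flatters the drug.* Under the stated conditions the tail falls too fast or the curve stops; it does not flatten.

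**Conclusion.** The documents contradict each other on how long 8-weekly assessment lasts, and this needs reconciling. The consequence for PFS arises only if 5.4 is followed over the other three statements and no adequate progression-free scan falls in the gap. Then progression or death after week 64 + 1 day is censored at week 48, and the curve beyond week 48 cannot be relied on.

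The exposed share is about 3.3% of patients at a 13-week median, 0.3% at 7.7 weeks, and about 11% and 18% at assumed medians of 20 and 26 weeks. These are upper bounds on the patients affected, because any intervening scan without progression takes a patient out of the count. They rest on exponential PFS and on reading the protocol's PFS figures as medians. Median PFS and disease control rate are not materially affected. Severity is low.

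**What to change.** Reconcile Protocol 5.4 with the synopsis, Appendix A footnote 5 and SAP 2.1 so that one imaging schedule governs PFS ascertainment. The smallest edit is to delete the one-year cap from 5.4, which then matches the other three statements. It changes one sentence and costs a few routine scans that those statements already call for. If the sponsor intends the cap, the other three places need to carry it, and SAP Appendix 1.3 must say how events after the last scheduled scan are handled.

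If conduct is complete, state in the SAP or study report which schedule sites followed, report how many patients hierarchy 3 censors after week 48, and add a PFS sensitivity analysis that counts those progressions and deaths as events on their documented dates. This needs no new data, only one extra derivation and one table.

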## 5.5 End of Study Evaluation

All patients will be followed for a minimum of 30 days after the last dose of BBI608. If a patient is removed from the study due to drug-related adverse events, the patient will be followed until resolution of any drug-related AE occurring during the study or within 30 days of the last BBI608 dose, or for 30 days, whichever is longer. In the presence of toxic effects, follow-up visits will be required every four weeks until all study related toxicities have resolved to baseline (or < Common Terminology Criteria for Adverse Events [CTCAE] Grade 1), stabilized or are deemed irreversible.

The following assessments will be made during the end of study visit:

- Physical examination
- Karnofsky performance status
- Vital signs (weight, temperature, blood pressure, respiration and pulse)
- Hematology (see Section 6.3)
- Blood chemistry (see Section 6.3)
- Liver function tests (see Section 6.3)
- Electrolytes (see Section 6.3)
- Urinalysis (see Section 6.3)
- 12-lead ECG
- Tumor marker, if applicable
- Tumor biopsy, if applicable (see Section 6.5.1)
- Tumor measurement and staging
- Assess adverse events
- Record concomitant medications

## 5.6 Discontinuation from Study

Patients will be removed from the study at any time if they meet any of the following criteria:

- Documented radiologic or clinical progression of disease
- Noncompliance with any part of the study, as evaluated by the Principal Investigator and Medical Monitor
- Withdrawal of consent
- Lost to Follow-up
- Death
- Clinically unacceptable toxicities despite optimal treatment.

## **6 STUDY PROCEDURES**

## 6.1 Medical History

Medical history will include but not limited to the following:

- Demography: date of birth, sex, ethnic origin, height, and weight
- Clinically significant prior diagnoses, surgeries, and current medications
- Prior cancer history, current cancer diagnosis, tumor stage at time of diagnosis and screening, previous chemotherapy, including dates and duration of treatment, level of response per RECIST and duration of response, previous radiation therapy, including anatomic site, dose and date of treatment
- Other patient characteristics will be summarized as appropriate

## 6.2 Physical Examination

Complete physical examination including height, weight, blood pressure, heart rate, respiratory rate, temperature (oral, axillary or tympanic) and Karnofsky performance status (Section 15).

